Cognitive Behavioral Therapy for Insomnia for Gulf War Illness

NCT02782780

Prepared: 12/09/2020

Study Protocol

I. Hypothesis: We hypothesize that telephone delivered cognitive behavioral therapy for insomnia (CBTi) will reduce insomnia and non-sleep Gulf War Illness (GWI) symptoms in Gulf War veterans with GWI. Specifically:

1. Effect sizes will suggest that 8-weeks of telephone CBTi improves measures of insomnia severity, subjective sleep quality, and sleep diary measures of total sleep time, sleep onset latency (i.e., the time it takes to fall asleep), and sleep efficiency.
2. Effect sizes will suggest that 8-weeks of telephone CBTi improves measures of non-sleep GWI symptoms, as assessed by the “symptom” portion of the Kansas Gulf War Military History and Health Questionnaire, and measures of fatigue, pain, cognitive dysfunction, and depression and anxiety.
3. In subjects randomized to the treatment arm of the trial, post-CBTi improvements in measures of insomnia and GWI symptoms will be maintained at the 6-month follow-up.

II. Aims:

1. Estimate effect size of telephone-delivered CBTi on insomnia and sleep quality in veterans with Gulf War Illness (GWI) and insomnia (i.e., have Insomnia Severity Index (ISI) scores ≥ 14).
2. Estimate effect size of telephone-delivered CBTi on GWI symptoms in veterans with GWI and ISI scores ≥ 14 .
3. Examine maintenance of telephone-delivered CBTi effects at 6-month follow-up.

III. Study Design: The project will test the efficacy of telephone-delivered CBTi for sleep and non-sleep symptoms associated with GWI by performing a randomized, parallel-group trial with GW Veterans who meet both the Centers for Disease Control and Prevention (CDC) case definition for Chronic Multisymptom Illness (CMI)⁴, the Kansas case definition for Gulf War Illness (GWI)⁵, and who have insomnia, operationalized as having ISI scores ≥ 14 .

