The study's goal is to randomize 80 eligible participants to get 64 participants who complete the trial. Half of the participants will be randomly assigned to receive telephone CBTi (TX). The other half will be randomized to a Monitor Only (MO) control group. Participants randomized to the TX group will receive 8 weekly sessions of CBTi via telephone with the study therapist. Participants randomized to the MO group will be monitored for 8 weeks (i.e., they will be advised to continue doing whatever they were doing to manage their GWI and insomnia symptoms without change dosage or frequency of treatment).

Prior to randomization, all subjects will be monitored for 1 week with sleep diary. Sleep diary data will also be acquired continuously throughout the 8 study-weeks in both groups. Outcomes will be assessed in all study participants at baseline (i.e., before randomization), mid- and post-treatment. In subjects randomized to TX, outcomes will be assessed once more, 6 months after treatment with Qualtrics online surveys or with traditional pen-and-pencil surveys.

Subjects randomized to the MO condition will be offered telephone-CBTi, at no cost to them, after 8 weeks of monitoring and upon completion of the post-treatment assessments.

Prior to the initiation of the study, we will conduct a test run of the study procedures in 2-6 GW veterans. To preserve our pool of eligible GW veterans for the CBT-I trial proper, for the test run, we will recruit GW veterans who have Insomnia Severity Index (ISI) scores > 12, and/or who screen positive for obstructive sleep apnea, and/or who do not meet the criteria for Kansas Gulf War Illness because of an exclusionary medical condition (e.g., seizures or heart disease).

IV. Procedures:

A. Subject Evaluations:

1. Screening for Inclusion: Once subjects have initiated contact, they will be given more information about the study by telephone or by US mail. An initial pre-screen will be performed over the telephone by a study staff member after subjects have given their verbal consent to determine inclusion/exclusion criteria.
2. Clinical Screening: If subjects pass the initial pre-screening for inclusion, they will participate in a clinical screening interview with an experienced clinical interviewer under the supervision of a licensed clinical psychologist. The clinical interviewer will be kept blind to treatment assignment. The following instruments will be used in the clinical screening interview:

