- PCL-5,⁸² a 20-item self-report measure that assesses the 20 DSM-5 symptoms of PTSD, will be used to monitor PTSD symptom change in subjects with PTSD.
- Sleep diaries will be used to allow the self-recording of various sleep-related measures such as time in bed (TIB), total sleep time (TST), wake after sleep onset (WASO), sleep onset latency (SOL, the time it takes to fall asleep). In addition, participant will be asked to log the nature and dose of all medications in their sleep diaries.

VI. Intervention:

- A. Cognitive Behavioral Therapy for Insomnia (CBTi) will be administered via telephone by therapists at the San Francisco VA Medical Center to participants for 8 weekly sessions.
- B. CBTi will consist of several sessions of sleep restriction, stimulus control and cognitive restructuring related to sleep concerns. The CBTi therapists will all have prior training in CBTi and will be supervised by study co-investigator [name], a licensed clinical psychologist with over ten years of experience in behavioral sleep medicine treatment and research.
- C. Monitor Only Waitlist Control condition will consist of continuous monitoring of sleep with diary and data collection at baseline, weeks 4 and 9.

D. Waitlist participants will receive weekly telephone or email check-ins from the study coordinator and will be offered CBTi following completion of the research protocol.

VII. Statistical Analysis:

- Linear mixed models with random effects for subjects will be used to analyze all available data for the intent-to-treat analysis. Because sex will be used as a stratification variable in the randomization procedure, it will not be included as a covariate in the analyses.
- Treatment effects will be estimated from post-treatment group differences using mixed models adjusting for baseline scores on each outcome. Standardized effect sizes will be calculated by dividing the treatment effect on each outcome variable by the pooled standard deviation of the variable at baseline.
- To compare baseline data to 6-month follow-up data in the CBTi group, planned contrasts following the mixed models will be used. Statistical analyses will be carried out using R (version 4.0.1). Mixed models will be fitted using the lme4 package (version 1.1-23) and significance tests will be based on Kenward-Roger degrees of freedom estimate provided by the pbkrtest package (version 3.1-2).

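### Do Hypotheses 1 and 2 rest on bare point effect sizes, because Section VII states no confidence interval, alpha or sidedness?

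*Combined protocol and SAP*

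**What the plan says.** Two purposes are stated for the same between-group comparison. Section III (Study Design) says "The project will test the efficacy of telephone-delivered CBTi for sleep and non-sleep symptoms associated with GWI". Section II (Aims) is worded as estimation: item 1 reads "Estimate effect size of telephone-delivered CBTi on insomnia and sleep quality in veterans with Gulf War Illness (GWI) and insomnia", and item 2 reads "Estimate effect size of telephone-delivered CBTi on GWI symptoms in veterans with GWI". Section I (Hypothesis) is worded cautiously. Item 1 begins "Effect sizes will suggest that 8-weeks of telephone CBTi improves measures of insomnia severity" and item 2 begins "Effect sizes will suggest that 8-weeks of telephone CBTi improves measures of non-sleep GWI symptoms". Neither says how large an effect must be.

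Section VII (Statistical Analysis) uses linear mixed models with subject random effects to "analyze all available data for the intent-to-treat analysis". The treatment effect is the post-treatment group difference adjusted for the baseline score. The effect size is that difference over the pooled baseline standard deviation: "Standardized effect sizes will be calculated by dividing the treatment effect on each outcome variable". The last bullet gives the software and says that significance tests use Kenward-Roger degrees of freedom. No section states a confidence interval, a significance level, or one- or two-sidedness.

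On size, Section III aims to "randomize 80 eligible participants to get 64 participants who complete the trial", with half assigned to each arm.

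**The concern.** Read strictly, the hypotheses make effect sizes the evidence of improvement, and the only definition of an effect size is a ratio with no measure of precision. The sentence on significance tests is not explicitly tied to Hypotheses 1 and 2, and it sits in the bullet that opens with the 6-month contrasts. Section III's efficacy wording adds to the unease, because an efficacy claim normally needs a stated error rate.

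If the report gave only point values, a small favourable effect could be presented as improvement when the data are also compatible with no effect. The open choice of sidedness also matters. At 32 per arm with no gain from baseline adjustment, the observed effect needed for significance at 0.05 is 1.96 × 0.25 = 0.49 SD two-sided and 1.645 × 0.25 = 0.41 SD one-sided.

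**Working it through.** **Inputs from the documents.** 80 randomized and 64 completers, allocated equally (Section III). This gives 40 per arm randomized and 32 per arm completing if losses are equal. The implied loss is 1 − 64/80 = 20%. No power, target effect, standard deviation or correlation is given, so there is no precision or power figure to reproduce.

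**Assumptions.** Baseline to post-treatment correlation r from 0 to 0.7; post-treatment SD equal to baseline SD, then relaxed; normal quantiles.

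**Step 1: does the planned model already supply what is missing?** The effect size is d = Δ/S, where Δ is the adjusted difference and S the pooled baseline SD. Since S is positive, d = 0 exactly when Δ = 0. The Kenward-Roger test of Δ is therefore also the test of a zero effect size. The same fit gives SE(Δ), and hence an interval Δ ± t × SE(Δ). Dividing its limits by S gives an approximate interval for d. No new model or data are needed.

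**Step 2: precision.** SE(d) = √[(2/n)(1 − r²)], and the 95% half-width is 1.96 × SE.

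| n per arm | r | SE | half-width (SD) |
|---|---|---|---|
| 32 | 0 | 0.250 | 0.49 |
| 32 | 0.5 | 0.217 | 0.42 |
| 32 | 0.7 | 0.179 | 0.35 |
| 40 | 0 | 0.224 | 0.44 |
| 40 | 0.5 | 0.194 | 0.38 |
| 40 | 0.7 | 0.160 | 0.31 |

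With t quantiles the range is 0.32 to 0.50. Entry requires an ISI score of at least 14 on a 0 to 28 scale, so the baseline ISI SD is range-restricted and the post-treatment SD may be larger. If it were 1.25 to 1.5 times the baseline SD (an assumption), the half-widths scale by the same factor: 1.25 × 0.313 = 0.39 at the narrow end and 1.5 × 0.490 = 0.74 at the wide end.

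**Step 3: would a stricter decision rule help?** One could call an outcome improved only if its 95% interval excludes zero favourably, and claim a whole hypothesis only if every listed outcome passes.

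- Hypothesis 1 lists five measures. Take a true d of 0.5 on each, 32 per arm and r = 0. Power per outcome is Φ(0.5/0.25 − 1.96) = Φ(0.04) = 0.516. For all five, if independent, it is 0.516⁵ = 0.037, about 4%. With a correlation of 0.5 between outcomes it is about 18%.
- Under the most favourable of the settings tried (40 per arm, r = 0.6), the figures are about 32% and 51%.
- For Hypothesis 2 the rule is not defined. The Brief Pain Inventory has no single named score in the plan, and the MASQ covers five domains.
- Used outcome by outcome without adjustment on about 11 measures (five in Hypothesis 1, about six in Hypothesis 2), the rule gives at least one false favourable call with probability 1 − 0.975¹¹ = 0.24 when nothing works and outcomes are independent. At a correlation of 0.5 between outcomes this is about 0.15.

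**The case for a change.** The strongest case for a change is that an estimation aim is not met by an estimate without a stated precision, and that nothing in the plan commits the analyst to an interval. The text supports this: interval, alpha and sidedness are absent, and the surrounding sentences of Section VII are intact, so redaction or text extraction does not explain the gap. The remedy is also cheap, a few sentences and a few lines of output. The one-sided against two-sided difference (0.41 against 0.49 SD) shows that the silence is not wholly empty.

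What stands is that Section VII is less explicit than it could be and that one phrase in Section III does not match the Aims. What does not stand is that the plan relies on a point value alone, because tests from the same model are planned alongside the effect sizes. Nor does the plan adopt any effect-size cut-off, so an error rate worked out for a chosen threshold would describe a rule that is not in it.

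**Conclusion.** No change is needed. Followed as written, Section VII gives a sound baseline-adjusted estimate, a valid test and a standard error from one model. Reporting 95% intervals and testing two-sided at 0.05 are the defaults an analyst would apply, so this is a gap that is filled sensibly in practice. The efficacy phrase in Section III is loose wording beside Aims and Hypotheses that speak of estimating and suggesting.

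The limited precision is real: about 0.31 to 0.49 SD either side for r from 0 to 0.7 with equal SDs, and up to about 0.74 SD if the post-treatment SD is 1.5 times baseline. It follows from the sample size, and an added sentence would not improve it. Going further, to pass/fail rules per outcome or per hypothesis, is a debatable trade-off. It sits badly with an estimation aim and could cut power to about 4% in the least favourable case examined. All these figures rest on assumed correlations, SDs and effects, since the documents give none.

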 - a. The Structured Clinical Interview for DSM-V (SCID-5¹⁵) will be used to assess DSM-V diagnostic criteria for Axis I disorders.
 - b. Clinician Administered PTSD Scale (CAPS⁵⁶) will be administered to all study participants to assess posttraumatic stress disorder (PTSD) status at baseline.
 - c. Addiction Severity Index-Lite (ASI-Lite) questionnaire will be used to obtain data on the participant's history of alcohol consumption and substance use.
 - d. Ohio State University Traumatic Brain Injury Identification Method (OSU TBI-ID⁶⁹) This is a standardized procedure to elicit the lifetime history of TBI for an individual. The instrument is based on CDC; National Center for Injury Prevention and Control (2003) case definitions and recommendations for TBI surveillance
 - e. Subjects will be screened with the Berlin Questionnaire to assess the likelihood of obstructive sleep apnea (OSA).
 - f. Subjects will be screened with restless legs syndrome screening questionnaire (RLSSQ)⁷⁵ to assess the likelihood of restless legs syndrome (RLS). An RLSSQ score ≥ 7 ,⁷⁵ identifies patients with RLS with 97.9% sensitivity and 96.2% specificity, will be dropped from the study.

If data from the clinical evaluation suggests that a subject is eligible for the study, the subject will be asked to keep a sleep diary for one week. Following that, the subject will be randomized to the CBT-I (TX) group or the Monitor Only (MO) group

B. STUDY ASSESSMENTS: The following assessments will be performed at baseline (i.e., before randomization), mid- and post-treatment in all participants. For participants randomized to TX, the assessments will be performed again 6-months after treatment.

1) The **Insomnia Severity Index (ISI⁷⁶)** is a 7-item self-report questionnaire assessing the nature, severity, and impact of insomnia in the last month. The dimensions evaluated are: severity of sleep onset, sleep maintenance, and early morning awakening problems, sleep dissatisfaction, interference of sleep difficulties with daytime functioning, noticeability of sleep problems by others, and distress caused by the sleep difficulties. A 5-point Likert scale is used to rate each item (e.g., 0 = no problem; 4 = very severe problem), yielding a total score ranging from 0 to 28.⁷⁶

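### Hypothesis 3 is about keeping the post-treatment gain, but the only planned 6-month contrast is against baseline

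*Combined protocol and SAP*

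**What the plan says.** Section I, item 3, predicts for the treated arm that "post-CBTi improvements in measures of insomnia and GWI symptoms will be maintained at the 6-month follow-up". Section II, item 3, sets the matching aim: "Examine maintenance of telephone-delivered CBTi effects at 6-month follow-up".

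The visits needed are scheduled. All participants are assessed at baseline, mid-treatment and post-treatment (Section III), and for the treated arm Section IV.B adds: "For participants randomized to TX, the assessments will be performed again 6-months after treatment". The Monitor Only arm has no 6-month assessment.

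Section VII names two comparisons. One is between groups and stops at the end of treatment: "Treatment effects will be estimated from post-treatment group differences using mixed models adjusting for baseline scores on each outcome". The other is the only one that uses the 6-month visit: "To compare baseline data to 6-month follow-up data in the CBTi group, planned contrasts following the mixed models will be used". No contrast of post-treatment with 6 months, no margin and no definition of maintained appears in the documents.

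**The concern.** In Hypothesis 3, what has to last is the improvement reached after CBTi, so the reference point is the post-treatment score. The planned contrast uses baseline as its reference and therefore answers another question: is the treated arm still better than when it started?

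If the plan is followed as written, the one prespecified 6-month result can be significant after much of the gain has gone, and it could then be taken as support for Hypothesis 3. Nothing in the plan commits the team to estimating how much was lost. Whether and how that is reported is left to choice after the data are seen.

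**Working it through.** **What the contrast measures.** For a treated participant, write B, P and F for the baseline, post-treatment and 6-month scores, with lower scores better. Then

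B − F = (B − P) + (P − F).

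The first term is the gain and the second is the later change, which is negative if symptoms return. The planned contrast estimates the sum. Hypothesis 3 concerns P − F. A positive sum is compatible with any loss smaller than the gain.

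**Can the missing term be estimated?** Yes. P and F are both scheduled in the treated arm, and Section VII says: "Linear mixed models with random effects for subjects will be used to analyze all available data for the intent-to-treat analysis". The gap is in prespecification, not in data collection.

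**Size, as an illustration.** The plan has no figure to reproduce here: it states no alpha, expected gain, SD of change or 6-month retention. The inputs are:

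- From Section III: "randomize 80 eligible participants to get 64 participants who complete the trial", with half allocated to each arm. That is 40 treated participants randomized, and 64 / 2 = 32 completing if losses are equal.
- Assumed: 32 is also the number of pairs at 6 months (24 and 40 as sensitivity values); ISI gain 6 points (4 as sensitivity); SD of change 4, 5 or 6, the same for both contrasts; two-sided 5%.

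The mixed model is approximated by a paired t-test on complete pairs. Power comes from the noncentral t distribution with n − 1 degrees of freedom and noncentrality δ√n / SD. If a share L of the gain is lost, δ = 6(1 − L) for the planned contrast and δ = 6L for the absent one. At half loss both are 3 points. With n = 32 the noncentralities are 3√32/4 = 4.24, 3√32/5 = 3.39 and 3√32/6 = 2.83.

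Probability of significance, n = 32, for SD 4 / 5 / 6:

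| Share of gain lost | Planned: baseline vs 6 months | Absent: post-treatment vs 6 months |
|---|---|---|
| A quarter | >0.99 / >0.99 / 0.98 | 0.54 / 0.38 / 0.28 |
| A half | 0.98 / 0.91 / 0.78 | 0.98 / 0.91 / 0.78 |
| Two thirds | 0.78 / 0.59 / 0.45 | >0.99 / 0.99 / 0.95 |

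The half-loss row is the same in both columns only because both effects are 3 points and the SDs are set equal.

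**Sensitivity at half loss, planned contrast.** With 24 pairs: 0.94 / 0.80 / 0.65. With all 40: >0.99 / 0.96 / 0.87. With a 4-point gain and 32 pairs: 0.78 / 0.59 / 0.45, so the problem is greater for larger gains.

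**Precision of the absent contrast.** The 95% CI half-width is t(0.975, n − 1) × SD / √n. At n = 32 and SD 4 it is 2.04 × 4 / √32 = 1.4 points; at SD 6 it is 2.04 × 6 / √32 = 2.2 points. That is 24% to 36% of a 6-point gain. The range is 1.7 to 2.5 points at n = 24 and 1.3 to 1.9 at n = 40.

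**The case against.** **Maintained may mean only still better than baseline.** Aim 3 read alone allows this, and the planned contrast would then serve it. Hypothesis 3 is narrower, because it names the post-CBTi improvements as what is kept. If the looser sense was intended, the plan should say so. The documents also nowhere state that a significant baseline contrast will be declared as maintenance; that risk is a conjecture about reporting.

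**The plural may cover more than one contrast.** The sentence names only baseline and 6 months, and with many outcomes the plural fits one contrast per outcome.

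**Relapse would be visible in the reported means.** Partly so, if they are reported. What is missing is a prespecified estimate of the change with its uncertainty.

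**The illustration rests on assumptions.** It does. Section III does not say whether completing the trial includes the 6-month survey, so 32 pairs at 6 months has no support in the documents. Equal SDs for the two contrasts are also assumed. The identity above does not depend on these inputs.

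**The added contrast is weak against small losses.** This stands. Without a margin it gives an estimate and no pass or fail on maintenance.

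**A stronger reading about the model.** A reader might infer that the Section VII model cannot yield the baseline contrast at all, because it adjusts for baseline, and that a separate treated-arm model is therefore required. The text does not support this. It says that baseline scores are adjusted for, but not that baseline is only a covariate. A joint longitudinal model can adjust for baseline while keeping it as an outcome time point.

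**Conclusion.** The concern holds as a mismatch between Hypothesis 3 and the one planned 6-month contrast. Confidence in the omission is high, since it rests on the text. A significant baseline contrast would show that some improvement remains, and no more. Under the assumptions above it would be significant with probability 0.78 to 0.98 after half the gain was lost, and 0.45 to 0.78 after two thirds was lost. These figures indicate scale and do not predict this trial.

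The reach is limited to the third aim, which is a within-arm comparison with no concurrent control. The randomized post-treatment comparison is unaffected, and nothing here suggests that the necessary visits are missing. It should be fixed.

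**What to change.** Amend Section VII as follows.

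1. For each outcome, prespecify the post-treatment to 6-month change in the treated arm, reported as an estimate with a 95% CI, as the main analysis for Hypothesis 3 and Aim 3.
2. Keep baseline versus 6 months as supportive.
3. State that a non-significant change will not be read as maintenance. Either prespecify a margin or call the result descriptive.
4. Label both results as uncontrolled within-arm comparisons.
5. State how baseline enters the model used for the 6-month contrasts. If it is only a covariate, that model cannot give the baseline contrast, so baseline should be an outcome time point, in either a treated-arm model or a joint longitudinal model.

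The cost is SAP wording, with no added visits, measures or participants. The downside is that maintenance becomes harder to claim: with a half-width of about 1.4 to 2.2 ISI points at 32 pairs, a loss of a quarter of a 6-point gain (1.5 points) may be neither shown nor excluded.

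### The only 6-month analysis stated compares the CBTi arm with its own baseline, which does not test the maintenance claimed in Hypothesis 3 and has no concurrent control

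*Combined protocol and SAP*

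**What the plan says.** Section I, item 3 predicts, for the CBTi arm, that "post-CBTi improvements in measures of insomnia and GWI symptoms will be maintained at the 6-month follow-up". Aim 3 in Section II is likewise about maintenance.

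Section VII gives one sentence to 6 months: "To compare baseline data to 6-month follow-up data in the CBTi group, planned contrasts following the mixed models will be used". It states no contrast between post-treatment and 6 months.

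Section III limits the 6-month data to one arm: "In subjects randomized to TX, outcomes will be assessed once more, 6 months after treatment". The control arm does not remain untreated: "Subjects randomized to the MO condition will be offered telephone-CBTi, at no cost to them, after 8 weeks of monitoring". Section VI.C has the Monitor Only arm assessed at baseline and at weeks 4 and 9.

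Entry is restricted to veterans "who have insomnia, operationalized as having ISI scores ≥ 14", and the ISI is also an outcome (Section IV.B, item 1). Eligibility checking begins by telephone: "An initial pre-screen will be performed over the telephone by a study staff member". Outcomes follow a separate description: "The following assessments will be performed at baseline (i.e., before randomization), mid- and post-treatment in all participants". The ISI is not among the clinical screening instruments listed in Section IV.A.2. No sentence says whether the qualifying ISI is reused as the baseline ISI.

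**The concern.** Maintenance is a statement about what happens between the end of treatment and 6 months. A contrast of 6 months with baseline answers another question: whether patients are still better than when they entered. If CBTi works well at first and then partly wears off, that contrast can be clearly significant and be reported as support for Hypothesis 3. This applies to every outcome and follows from the text alone.

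A second weakness is that the contrast is uncontrolled. Any fall from baseline mixes lasting benefit with natural course. For the ISI it may also contain regression to the mean, because patients were admitted on a high ISI. At stake is the conclusion on one of the three aims, the durability of the effect.

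**Working it through.** **1. Reference points.** Hypothesis 3 starts from post-treatment. The Section VII contrast starts from baseline. The two agree only if the change from post-treatment to 6 months is itself examined, and no such analysis is stated.

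**2. Sample size.** Section III plans to "randomize 80 eligible participants to get 64 participants who complete the trial", half in each arm. 64/80 = 0.80, and 64/2 = 32 CBTi completers. The documents give no ISI mean, SD, correlation, significance level or expected effect, so everything below is assumed: pre-selection mean 16, SD 5, correlation 0.6 between occasions unless stated otherwise, and a two-sided 5% paired test with n = 32 (critical t on 31 df = 2.04).

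**3. Can the stated contrast be significant after half the gain is lost?** Assume a gain of 4 points at post-treatment and 2 points left at 6 months.
- Separate baseline ISI, constant correlation: SD of change = 5 × √(2 × (1 − 0.6)) = 4.47; SE = 4.47/√32 = 0.79; 2/0.79 = 2.53. Chance of significance ≈ Φ(2.53 − 2.04) = Φ(0.49) = 0.69. Simulation gives 68% to 69%.
- Entry ISI is the baseline: expected fall = 2 + 1.02 (step 4) = 3.02; simulated SD of change 4.21; SE = 4.21/√32 = 0.74; 3.02/0.74 = 4.08. Chance ≈ Φ(4.08 − 2.04) = Φ(2.04) = 0.98. Simulation gives about 98%.

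**4. Regression to the mean in the ISI contrast.** For an integer score the cut-off is 13.5. k = (13.5 − 16)/5 = −0.5; λ = φ(k)/(1 − Φ(k)) = 0.352/0.691 = 0.509; mean excess of the entry score after selection = 5 × 0.509 = 2.55 points.
- Entry ISI is the baseline: spurious fall = (1 − r) × 2.55, where r is the correlation with the 6-month score. At r = 0.6 this is 0.4 × 2.55 = 1.02 points; at r = 0.8, 0.51; at r = 0.9, about 0.25. Over means 12 to 20, SDs 4 to 6 and r 0.5 to 0.7, the range is 0.13 to 2.9.
- Separate baseline ISI: spurious fall = (correlation of screening with baseline − correlation of screening with 6 months) × 2.55. With the 6-month correlation at 0.6:

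| Screening–baseline correlation | Spurious fall (points) |
|---|---|
| 0.6 (constant over time) | 0 |
| 0.7 | 0.1 × 2.55 ≈ 0.25 |
| 0.8 | 0.2 × 2.55 = 0.51 |
| 0.9 | 0.3 × 2.55 ≈ 0.76 |

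With no benefit left at 6 months, the paired test is significant in about 26% of trials if the entry ISI is the baseline. With a separate ISI the rate is 5% at constant correlation and about 9% at a screening–baseline correlation of 0.8.

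**5. What the post-treatment to 6-month contrast can do.** With the correlation between those two visits at 0.6, its SE is again 0.79. Power for a 2-point loss is Φ(2/0.79 − 2.04) = 0.69, or about 70%. The 95% CI half-width is 2.04 × 0.79 = 1.6 points. If correlation with the entry score falls from 0.7 at week 9 to 0.6 at 6 months, a drift of (0.7 − 0.6) × 2.55 ≈ 0.25 points downward remains, which would hide a little of any loss.

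**The case against.** Hypothesis 3 is worded for the treated arm only, so a within-arm analysis is what it calls for. That stands, and no 6-month control group is asked for here. It does not rescue the choice of reference point.

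A reader of the results could set the post-treatment and 6-month estimates side by side and judge maintenance by eye. That is possible, but without an interval on their difference it is not an analysis of it. Section VII does write of contrasts in the plural, but the comparison that it names is baseline against 6 months.

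On the ISI, a reader might infer that the 6-month result necessarily contains regression to the mean. The documents do not support that. The telephone pre-screen, the absence of the ISI from the listed screening instruments and its place among the baseline outcomes all lean toward a separate baseline ISI, without establishing one. With a separate ISI and constant correlation the expected drift is zero. Nor can one say that a separate ISI merely halves the drift: that rests on picking a screening–baseline correlation of 0.8. Some drift is still plausible, because the ISI asks about the last month and two early scores may share recall time.

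The plan is also not without information on drift. The Monitor Only arm passes the same entry filter and is measured to week 9. What is missing is a stated use of those data and any control beyond that point. Finally, the false-positive rates assume that the benefit has vanished completely, which is an extreme case.

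**Conclusion.** The point holds, and its firm part is the mismatch between hypothesis and contrast. It needs no numerical assumption and covers every outcome: a significant change from baseline does not show that post-treatment gains were kept. The 68% to 98% figure illustrates this under assumed inputs only.

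The regression-to-the-mean part is conditional and specific to the ISI. It is present for any correlation below 1 if the entry ISI is the baseline (about 1 point under the central assumptions). Otherwise it is anywhere from nothing upward. Whichever applies, the change is uncontrolled.

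A reader might go further and doubt the main efficacy results. That would be wrong: the post-treatment comparison in Aims 1 and 2 is randomized, and both arms passed the same filter. This is a cheap improvement to the analysis of Aim 3.

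**What to change.** In Section VII:

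- Make the CBTi-arm contrast from post-treatment to 6 months, with a 95% CI, the analysis for Hypothesis 3 on every outcome.
- Keep the baseline to 6-month contrast, label it uncontrolled, and say that it will not be read alone as evidence of maintenance.
- State whether the ISI used for entry is also the baseline ISI.
- Optional: report the Monitor Only change from baseline to week 9 beside the 6-month result, as a rough guide to drift. It covers only the first weeks, so it cannot stand in for a 6-month control.

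The cost is a few sentences and one extra contrast from data already collected, with no new visits. The drawback is limited precision. With power of only about 70% for a 2-point ISI loss, a non-significant result does not prove maintenance. The report should interpret the interval, roughly ±1.6 points under the assumptions above, and not the p-value.
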